1.0 PROTOCOL SUMMARY AND SCHEMA

This is a study utilizing the hypoxia tracer fluorine-18-labeled fluoro-misonidazole (^{18}F -FMISO) to evaluate the presence and bio-distribution of tumor hypoxia in head and neck cancer patients. Two cohorts of patients will be accrued to this protocol:

- Cohort 1 will consist of 150 head and neck cancer patients over a 5-year accrual period who are not expected to undergo surgical resection of their cancer. This cohort will consist of 100 patients with Human Papilloma Virus positive (HPV+) tumors and 50 patients with Human Papilloma Virus negative (HPV-) tumors.
- Cohort 2 will consist of 19 head and neck cancer patients who will undergo surgery for their cancer per standard of care.

When possible, we will also obtain multi-parametric magnetic resonance (MR) scans consisting of conventional anatomical MR imaging (e.g. T1- and T2-weighted), diffusion-weighted MR imaging (DW-MRI), and dynamic contrast enhanced magnetic resonance imaging (DCE-MRI). These MR scans will be utilized to assess changes in MR intensities and the perfusion and diffusion of water molecules in tumor and irradiated normal structures during and after the course of fractionated external beam radiation therapy (RT). The DCE-MRI data will provide insight into the tumor pathophysiology. With proper compartmental modeling, the DCE-MRI data will yield results on tumor-vessel permeability, tumor perfusion, and extracellular-extravascular volume fraction, i.e. data relating to the tumor microenvironment. These results will determine the potential of DCE-MRI data as a priori or early markers of tumor response to chemoradiation as well as long term disease-free survival after treatment.

This study will further entail the first human study of ^{18}F -FMISO PET image-guided core biopsy of neck node(s) in both HPV+ and HPV- head and neck squamous cell carcinoma (HNSCC; for Cohort 1 patients that consent to this optional biopsy). Additional tissue will be collected from patients who will undergo surgical resection of their cancer per standard of care (Cohort 2). We will correlate the intensity of the ^{18}F -FMISO PET signal with the degree of immunohistochemical staining of the following hypoxia biomarkers, among others: HIF-1 α , Lysyl Oxidase, and Ki67 (an independent marker of tumor aggressiveness).

Lastly, this study will evaluate a number of treatment approaches to HPV-related head and neck cancer. The approaches applicable to Cohort 1 of this study are outlined below:

1. Definitive chemoradiation without pretreatment surgical resection in which both the primary tumor site and the neck nodes receive 70Gy. In patients who exhibit a complete nodal response with this treatment, no further treatment is necessary.
2. Definitive chemoradiation without pretreatment surgical resection in which the primary site receives 70Gy while the neck nodes receive a lower dose of radiation at 60Gy instead of 70Gy. This definitive chemoradiation is followed by a FDG PET/CT scan at 3 months (+/- 4 weeks) post-treatment. In patients who exhibit a

complete nodal response with this method of treatment (as determined by the 3-month post-treatment FDG PET/CT scan), no further treatment is necessary.

Patients enrolled on to this protocol who will receive either of the treatments above (i.e. those without surgical resection of their cancer) will be included in Cohort 1, and will continue with standard institutional care in the case of incomplete or no nodal response. The information obtained from the use of ^{18}F -FMISO PET scans in Cohort 1 will be used to guide these patients' treatment on this protocol. HPV+ head and neck cancer patients in Cohort 1 that exhibit no evidence of hypoxia on their baseline ^{18}F -FMISO PET scan and HPV+ head and neck cancer patients in Cohort 1 with early resolution of hypoxia on their repeat ^{18}F -FMISO PET scan will receive 70Gy to the primary site and 60Gy to the neck nodes followed by a FDG PET/CT scan and observation.

Cohort 2 of this protocol will consist of patients who are to receive surgical resection of their tumor. Following this surgery, patients may or may not undergo adjuvant radiation with or without concurrent chemotherapy, which is dependent on the pathologic features of their disease. Within this cohort, select HPV+ tumors that demonstrate no evidence of hypoxia on a ^{18}F -FMISO PET scan will receive 30Gy to the surgical bed and neck lymph nodes concurrent with standard chemotherapy followed by a 3 to 4-month post-treatment neck dissection. In patients who exhibit a complete response with this method of treatment, no further treatment is necessary. For patients within this select group who still have pathologic nodal disease, further standard chemoradiation will be given. All other patients in this cohort (i.e. those who are not in the select HPV+ tumor group outlined above) will receive standard of care treatment following their surgery.

Please note the ^{18}F -FMISO PET imaging protocol is exactly the same for all patients on this protocol, regardless of cohort.

Schema:

- 1.1 Evaluation, determination of cohort, and consent.
- 1.2 Baseline studies (standard of care) for head and neck cancer.
- 1.3 Perform a pretreatment FDG PET/CT scan for Cohort 1 patients.
- 1.4 Perform a recommended pretreatment multiparametric MRI scan for Cohort 1 patients. This scan will be used to derive a pixel-by-pixel mapping of true diffusion (D), perfusion fraction (f), and apparent diffusion coefficient (ADC) using available software when available (unless contraindicated; for main campus only).
- 1.5 Prior to the injection of the ^{18}F -FMISO radiotracer, check the patient's vital signs.

- 1.6 Perform a pretreatment dynamic ^{18}F -FMISO PET/CT scan. This scan will be used to verify the constancy of the hypoxic regions within the gross tumor volume (GTV_h).
- 1.7 A safety assessment will be performed: vital signs and a toxicity assessment will be completed immediately after the scan session, and a follow-up phone call to assess for toxicities will be done on the next business day following the ^{18}F -FMISO PET/CT scan (excluding holidays and weekends).
- 1.8 An ^{18}F -FMISO PET image-guided core biopsy procedure of the neck nodes will be performed after the last ^{18}F -FMISO PET image acquisition for Cohort 1. This biopsy procedure will only occur if the patient consents to the procedure and if the procedure is deemed applicable by the Principal Investigator.
- 1.9 Surgical resection for Cohort 2 (if it has not already occurred) and collection of the resected tissue for the correlation of ^{18}F -FMISO PET/CT signal with the degree of immunohistochemical staining of hypoxia biomarkers.
- 1.10 Prior to the injection of the ^{18}F -FMISO radiotracer for the repeat ^{18}F -FMISO PET/CT scan for patients deemed eligible for a repeat ^{18}F -FMISO PET/CT scan, check the patient's vital signs.
- 1.11 Perform a repeat dynamic ^{18}F -FMISO PET/CT scan early during the course of chemoradiotherapy (5-10 treatment days after the start of radiation therapy) for patients deemed eligible for a repeat ^{18}F -FMISO PET/CT scan. This scan will be utilized to determine whether there is a reduction of the ^{18}F -FMISO-avid or GTV_h within the gross tumor volume.
- 1.12 A safety assessment will be performed for patients who received a repeat ^{18}F -FMISO PET/CT scan: vital signs and a toxicity assessment will be completed immediately after the scan session, and a follow-up phone call to assess for toxicities will be done on the next business day following the ^{18}F -FMISO PET/CT scan (excluding holidays and weekends).
- 1.13 An ^{18}F -FMISO PET image-guided core biopsy procedure of the neck nodes will be performed after the last ^{18}F -FMISO PET image acquisition for Cohort 1. This biopsy will only occur if the patient consents to the procedure and if the procedure is applicable as determined by the Principal Investigator.
- 1.14 Perform recommended approximately weekly MRI scans during treatment, unless contraindicated, for main campus Cohort 1 patients. A DCE-MRI is recommended between the first and second weeks of

treatment and between the third and fourth weeks of treatment, unless contraindicated, for main campus Cohort 1 patients. Subjects with a known contraindication to the standard MRI contrast agent (Gadavist; a gadolinium-based contrast agent) and/or a recent estimated glomerular filtration rate (eGFR) of 30 or less will be excluded from all recommended DCE-MRIs, and will instead receive recommended non-contrast MRIs at the DCE-MRI time points.

- 1.15 Recommended MRI scans, unless contraindicated, will also be repeated at 3 months, 6 months, and 1 year post-external beam RT for Cohort 1 patients. The time windows for these MRI scans will be +/- 4 weeks. Only Cohort 1 patients on main campus will receive these recommended MRIs.
- 1.16 Perform a FDG PET/CT scan at 3 months (window +/- 4 weeks) post-RT for Cohort 1 patients. Perform a planned neck dissection at three to four months (+/- four weeks) post-RT for Cohort 2 patients who received 30Gy.
- 1.17 Standard of care follow-up.
- 1.18 Longitudinal chart review for adverse event assessment, locoregional control rates, and disease status as assessed through standard of cares through two years post-treatment for Cohort 1 and Cohort 2.

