We have performed preliminary clinical studies with ^{18}F -FMISO obtaining PET images at 2.5 hours post-injection for 20 head and neck cancer patients (MSKCC 04-070). These studies focused first on determining the constancy of ^{18}F -FMISO PET image sets when repeat scans were performed 3 days apart (an essential pre-requisite for IMRT dose painting). Preliminary results demonstrated that imaging of hypoxic subvolumes (GTV_h) is feasible and that reproducible zones of hypoxic tracer uptake are observed (7). We also performed a third ^{18}F -FMISO scan on patients at four weeks into their radiotherapy treatment (MSKCC 04-070). The objective of this third scan was to determine whether tumor reoxygenation occurred, as indicated by no ^{18}F -FMISO uptake, or whether hypoxia persisted throughout treatment. Our finding from this second clinical study objective, as evidenced by 18/20 patients exhibiting no ^{18}F -FMISO uptake, was that hypoxia is no longer evident late into a course of radiotherapy. Patients in this cohort experienced at 95% nodal control rate (9). The possibility of tumor reoxygenation early during the course of fractionated radiotherapy cannot be overlooked. Therefore, in the current version of this protocol, our goal is to perform a repeat ^{18}F -FMISO PET/CT scan early in the course of standard chemotherapy and fractionated radiotherapy (5 to 10 treatment days) for a series of locally advanced head and neck cancer patients (Cohort 1). If these repeat scans also demonstrate no evidence of residual ^{18}F -FMISO uptake early in the course of fractionated radiotherapy, this information will have major implications for hypoxia-guided fractionated radiotherapy.

In summary, hypoxia is a characteristic feature of malignant tumors that can render tumor cells up to three times more resistant to ionizing radiation than aerobic cells. With the use of ^{18}F -FMISO PET, a noninvasive imaging modality, hypoxic subvolumes (GTV_h) within a tumor can be identified. If these hypoxic regions are identified and verified, they may be specifically targeted by the delivery of more ionizing radiation to that

specific region. Ultimately, by the delivery of a differential dose of radiation to the tumor, the local control rates of head and neck cancer patients may further be improved.

Multiparametric MRI

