4.0 OVERVIEW OF STUDY DESIGN AND INTERVENTION

4.1 Design

PROTOCOL SUMMARY

TIMEPOINT	COHORT 1	COHORT 2
Pretreatment	All Patients	All Patients

	
1) Patient simulation. 2) FDG scan with immobilization. 3) Recommended pretreatment MR scan with immobilization when possible (unless contraindicated, for main campus only). 4) ¹⁸F-FMISO scan (only 1 injection). Patient injected on the PET scanner: (a) Dynamic scan from 0-45 min (b) 10 min scan at about 90 min (c) 10 min scan at about 150-180 min 5) ¹⁸F-FMISO image-guided core biopsy (optional, if consented)
	
1) ¹⁸F-FMISO scan (only 1 injection). Patient injected on the PET scanner: (a) Dynamic scan from 0-45 min (b) 10 min scan at about 90 min (c) 10 min scan at about 150-180 min

During Treatment	
Select Patients
 
1) Repeat ¹⁸F-FMISO scan (only 1 injection) that occurs 5-10 treatment days after RT start*. Patient injected on the PET scanner: (a) Dynamic scan from 0-45 min (b) 10 min scan at about 90 min (c) 10 min scan at about 150-180 min 2) ¹⁸F-FMISO image-guided core biopsy (optional, if consented) 3) Recommended approximately weekly MRI when possible (unless contraindicated, for main campus only). Recommended DCE-MRI between treatment weeks one and two and between treatment weeks three and four, when possible.
	
Patients who Receive Radiation
 
1) Repeat ¹⁸F-FMISO scan (only 1 injection) that occurs 5-10 treatment days after RT start*. Patient injected on the PET scanner: (a) Dynamic scan from 0-45 min (b) 10 min scan at about 90 min (c) 10 min scan at about 150-180 min

Post-treatment	
All Patients
 
1) Recommended MR Scans at 3, 6, and 12 months (+/- 4 weeks) post end of RT (unless contraindicated, for main campus only) 2) Longitudinal chart review for two years post RT for adverse event assessment and disease status
	
Patients Who Receive 30Gy
 
1) Neck dissection three to four months post-chemoradiation (+/- 4 weeks). (a) If no residual disease, standard of care (b) If residual disease, booster dose of chemoradiation 2) Standard of care

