The original approved protocol MSKCC 04-070 consisted of 3 injections of 370 MBq of ¹⁸F-FMISO per patient. The current protocol involves up to 2 injections of 370 MBq of ¹⁸F-FMISO per patient. The dose estimates derived from the University of Washington data were used to provide the dose from the single 10 mCi administration of ¹⁸F-FMISO and were confirmed by our pilot study. The urinary bladder wall is subject to the largest dose of 0.78 cGy. This is an insignificant addition to the total therapeutic radiation dose that the patient will receive for his or her head and neck cancer. In addition, the patient will receive a low dose CT attenuation scan each contributing an addition of 0.9 cGy whole body dose to the patient. The dose to the eyes from the combination of an ¹⁸F-FMISO and CT scan would be $0.57 + (3 \times 0.9)$ cGy = 3.27 cGy. This will also not significantly add to the total radiation dose that the patient will receive from treatment for his or her head and neck cancer.

Also note that these radiation doses are overestimates, because the CT scan (and therefore dose) will only apply to a single 15cm field of view surrounding the lesion of interest. For example, for patients in which the lesion is remote from the eye, the lens will only receive a dose of 0.57 cGy resulting from the ¹⁸F-FMISO administration and nothing from the CT.

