9.0 TREATMENT/INTERVENTION PLAN

For patients in Cohort 1, there will be no change or intervention in a patient's treatment regime using chemoradiation where both the primary and the neck nodes receive 70Gy if the tumors are not associated with HPV or if there is no resolution of hypoxia on their repeat ¹⁸F-FMISO PET/CT scan.

Patients in Cohort 1 with tumors that are positive for HPV who exhibited no evidence of hypoxia on their baseline ¹⁸F-FMISO PET/CT scan or whose tumors have early resolution of hypoxia on their repeat early response ¹⁸F-FMISO PET/CT scan will undergo an alternative treatment where the primary tumor site receives 70Gy while the neck nodes receive 60Gy followed by a planned FDG PET/CT scan and observation.

Select Cohort 2 HPV+ tumors that demonstrate no evidence of hypoxia on an ¹⁸F-FMISO PET scan will receive 30Gy to the surgical bed and neck lymph nodes concurrent with standard chemotherapy followed by a 3 to 4 month post-treatment neck dissection. In patients who exhibit a complete response with this method of treatment, no further treatment is necessary. For patients within this select group who still have pathologic nodal disease, further standard chemoradiation will be given. All other patients in this cohort (i.e. those who are not in the select HPV+ tumor group outlined above) will receive standard of care treatment following their surgery.

Please note that for patients who receive a repeat ¹⁸F-FMISO PET/CT scan, the repeat ¹⁸F-FMISO PET/CT scan will only be performed 5-10 days into chemoradiotherapy treatment. For Cohort 1 patients, a repeat ¹⁸F-FMISO PET/CT scan will only be performed if the pretreatment baseline ¹⁸F-FMISO PET scan is positive for hypoxia.

Chemotherapy will be administered in two doses. Chemotherapy will begin +/- 3 days from the first day of radiation therapy. The second cycle of chemotherapy will begin 3 weeks later (+/- 5 days), although delays for safety (e.g, low white blood count, elevated creatinine) are allowed. Standard chemotherapy with either Cisplatin or Carboplatin/5-Fluorouracil is strongly recommended. Any other schedule (e.g, weekly chemotherapy) is discouraged and requires approval of the principal investigator.

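### One pretreatment FMISO session cannot verify constancy, and rescanning only baseline-positive Cohort 1 patients biases the measured change toward reduction by an amount the plan does not estimate

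*Combined protocol and SAP*

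**What the plan says.** Section 1.0, step 1.6, gives the purpose of the pretreatment dynamic FMISO PET/CT: "This scan will be used to verify the constancy of the hypoxic regions within the gross tumor volume".

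The table in Section 4.1 provides one pretreatment session: "scan (only 1 injection). Patient injected on the PET scanner". Its three acquisitions (0-45 min, about 90 min, about 150-180 min) follow that same injection. Section 5.0 sets the ceiling: "The current protocol involves up to 2 injections of 370 MBq of" FMISO per patient. The second injection is the on-treatment rescan at 5-10 treatment days. For the predecessor, the same section says: "The original approved protocol MSKCC 04-070 consisted of 3 injections of 370 MBq of" FMISO. Section 3.0 explains that 04-070 assessed constancy "when repeat scans were performed 3 days apart" and reports, in qualitative terms only, that the zones of uptake were reproducible.

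Section 9.0 limits the Cohort 1 rescan: it "PET/CT scan will only be performed if the pretreatment baseline" scan is positive for hypoxia. Cohort 2 carries no such condition; in Section 4.1 its rescan falls under "Patients who Receive Radiation".

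The second primary objective in Section 2.0 is to detect a reduction of the FMISO-avid or hypoxic volume in Cohort 1. Section 14 summarises the volume changes and expects 40 of the 50 HPV-negative patients to need a rescan. It treats a scan as negative or resolved when uptake is absent or has disappeared. It gives no repeatability limit, untreated comparison or allowance for measurement variation.

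**The concern.** Constancy means agreement between two scans with no treatment between them. The current schedule has no such pair, so step 1.6 keeps a task whose second scan has been dropped.

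The second part concerns how patients enter the change analysis. A patient near the positivity threshold may fall on either side of it at any one scan. Those who happen to read positive are rescanned, and some will then read negative. Those who happen to read negative are not rescanned, so the opposite crossings are never seen. The rescanned group therefore tends to drift downward even if chemoradiation has no early effect.

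At stake is the reading of a primary objective. Section 3.0 says that absence of residual uptake early in treatment would have major implications for hypoxia-guided radiotherapy. As planned, the report would not show how much of the observed fall is expected from scan variation alone.

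**Working it through.** **No figure to reproduce.** The documents give no sample size, power, standard deviation or error rate for the reduction objective.

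**Constancy, by comparison of sections.** Predecessor: up to three injections, including an untreated repeat 3 days apart. Current plan: one untreated injection and at most one on treatment. The three acquisitions in one session show tracer kinetics over hours, not stability over days. No current patient contributes an untreated pair.

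**Size of the bias: inputs**
- Baseline positivity 40/50 = 0.80, inferred from the HPV-negative rescan estimate in Section 14. Alternative: 14/15 = 0.93, from the outside tirapazamine study in Section 3.0.
- Baseline positivity in HPV-positive patients is not stated; 0.50 is an assumed low value.
- Test-retest correlation r is not stated; 0.95 to 0.50 is assumed.
- Model: the two measurements are standard bivariate normal with no true change and the same cut-off c at both scans, where P(X1 > c) = baseline positivity p. For p = 0.80, c = -0.8416.

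**Formulas**
- Share of baseline positives reading negative at rescan = 1 - P(X1 > c, X2 > c)/p.
- Mean change among baseline positives = -(1 - r) × φ(c)/p. For p = 0.80, φ(c)/p = 0.350.

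**Results for p = 0.80.** The last column is the smallest number of resolutions in 40 whose upper binomial tail, at that no-effect share, is at most 0.025.

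| r | P(both positive) | Share resolved | Of 40 | Mean change (SD) | Count exceeding chance |
|---|---|---|---|---|---|
| 0.95 | 0.7646 | 4.4% | 1.8 | -0.017 | 6 |
| 0.90 | 0.7499 | 6.3% | 2.5 | -0.035 | 7 |
| 0.80 | 0.7290 | 8.9% | 3.5 | -0.070 | 8 |
| 0.70 | 0.7129 | 10.9% | 4.4 | -0.105 | 10 |
| 0.60 | 0.6992 | 12.6% | 5.0 | -0.140 | 10 |
| 0.50 | 0.6872 | 14.1% | 5.6 | -0.175 | 11 |

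Example at r = 0.90: 1 - 0.7499/0.80 = 0.063, and 40 × 0.063 = 2.5.

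**Where the opposite crossings go.** At r = 0.90, 25% of baseline negatives would read positive on a second scan. Among the 10 unscanned HPV-negative patients that is 10 × 0.25 = 2.5, which exactly balances the 2.5 apparent resolutions. The plan observes only one side.

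**Sensitivity to positivity.** Over the same range of r, the no-effect share is 1.7% to 5.2% at 14/15 positive and 10.1% to 33.3% at 50% positive.

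**Illustrative test.** The plan states no test for reduction. If a one-sided signed-rank test at 0.025 were applied to 40 baseline-positive patients (p = 0.80, no true change, 2,000 simulated trials per setting), it would declare a reduction in 4.9% of trials at r = 0.95, 6.9% at 0.90, 11.0% at 0.80 and 13.5% at 0.60. With all 50 patients rescanned, the rate was 1.9% to 3.2% across all settings.

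**The case against.** **The bias is small beside a plausible effect.** This largely stands. A reader might infer that the objective cannot separate reoxygenation from scan variability at all, or that any reduction seen is artefact. The documents do not support either reading. Even at r = 0.50, 11 resolutions in 40 (27.5%) would exceed the no-effect rate. Section 3.0 reports no uptake in 18 of 20 patients at four weeks, and resolution in nearly all of 14 within 4-5 weeks in the outside study. Those scans are later than 5-10 treatment days, so they do not settle the early effect.

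**The filter is not protocol-wide.** Correct. It applies to Cohort 1, which carries the objective. Cohort 2 patients who receive radiation are rescanned without that condition, but resection normally falls between their scans, so they cannot act as a repeatability control.

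**Volume can rise as well as fall.** Correct. Only crossings of the positivity threshold are seen in one direction. Continuous change among rescanned patients moves both ways, with a modest downward mean bias.

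**Reproducibility was already shown.** In part. Section 3.0 describes reproducible zones, which makes the lowest correlations less likely, but it gives no limit or correlation. Section 4.1 calls uptake at the fixed 2.5-hour time point variable.

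**The magnitude is modelled.** Correct. The correlation is assumed, and a normal variable with a fixed cut-off stands in for a definition based on disappearance of uptake.

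**The 1.6 sentence is editorial.** Probably: constancy is not an objective and is not analysed in Section 14. Correcting it is still needed, because it credits the design with a check it does not contain.

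**Conclusion.** The point holds in a limited form. Step 1.6 cannot be carried out with one pretreatment session; this follows from the text without modelling. For the second primary objective, the baseline-positive entry condition in Cohort 1 pushes both the raw mean change and the resolution proportion toward reduction whenever repeatability is imperfect, and nothing in Section 14 allows for it.

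The direction is established; the size is not. At 80% baseline positivity and no true change, the assumed correlations imply about 2 to 6 false resolutions in 40. The figure is smaller if positivity is near 93% and larger if HPV-positive positivity is nearer 50%, which the documents do not state. The practical consequence is for small early effects: a handful of resolutions, or a mean fall of a tenth or two of an SD, could not be told from scan variation. The correction is worth making, but the objective is not invalidated.

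**What to change.** 1. **Step 1.6:** remove the constancy task and describe the scan as the baseline measurement of hypoxia.
2. **Section 14, repeatability:** from the untreated 3-day scan pairs of MSKCC 04-070, estimate the repeatability limit for late static uptake and hypoxic volume, and the positive-to-negative flip rate among patients positive on the first scan. Give each with a 95% interval.
3. **Section 14, second primary objective:** report the observed changes and the resolution proportion beside these two quantities. Describe falls within the limit as not distinguishable from scan variation.
4. **Limitation:** state that baseline-negative Cohort 1 patients are not rescanned and that regression to the mean therefore favours reduction.

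This changes analysis and reporting only. The definition of resolution in Section 14 and the assignment of treatment stay as they are, and the limit is not a new cut-off competing with that definition.

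**Cost.** A modest re-analysis with no new scans, provided the 04-070 pairs can be retrieved in usable form, which the documents do not confirm. The series had 20 patients, so the flip rate will be imprecise: even 0 flips in 20 gives an upper 95% limit of 1 - 0.025^(1/20) = 16.8%, which is why the interval must be shown. Fewer patients will count as clearly reduced. The limit rests on static images at 2.5 hours, against about 150-180 minutes here, and does not cover the dynamic k3 value.
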